PROTOCOL TITLE: Comparison of Ambu Auragain and I-Gel Supraglottic Airways in Adult Patients at an Ambulatory Surgery Center

VERSION DATE: 4/3/2021

1.0 Objectives

- 1.1** Purpose: The purpose of this study is to determine if an I-gel LMA has a higher oropharyngeal leak pressure compared to an Ambu Auragain in adult patients in an ambulatory surgery center.

2.0 Background

- 2.1** Significance of Research Question/Purpose: This study will help to determine if the use of I-gel LMA has a clinical advantage over the Ambu Auragain LMA.
- 2.2** Preliminary Data: Existing Literature: A previous study in pediatric patients demonstrated that I-gel has a higher OLP compared to Ambu auragain. A study performed in adult patients undergoing laparoscopic surgery demonstrated no significant difference between the two LMAs OLP. No studies have compared the two in a multispecialty ambulatory surgery center in patients undergoing general non laparoscopic surgery.

3.0 Study Endpoints/Events/Outcomes

- 3.1** Primary Endpoint/Event/Outcome: OLP immediately after placement
- 3.2** Secondary Endpoint(s)/Event(s)/Outcome(s): Time to placement, insertion attempts, first attempt success rate, ease of insertion, number of mid case adjustments, sore throat upon discharge from recovery room and at 24 hours after surgery analyzed using NRS 0-10 scale, and blood staining of LMA.

4.0 Study Intervention(s)/Investigational Agent(s)

- 4.1** Description: Patients who are scheduled for elective ambulatory surgery under general anesthesia will be randomized to one of two groups. Group 1 will receive an I-gel LMA and group 2 will receive an Ambu Auragain LMA.
- 4.2** Drug/Device Handling: The I-gel and Ambu auragain will be stocked in the anesthesia carts as they currently are.
- 4.3** Biosafety: N/A
- 4.4** Stem Cells: N/A

5.0 Procedures Involved

- 5.1** Study Design: This is a level I randomized prospective outcomes study comparing two groups of patients. All patients scheduled for general anesthesia at the M Health Ambulatory Surgery Center who are appropriate for an LMA will be approached for the study. Once enrolled patients will be randomized 1:1 between the groups based on a randomization schedule generated before study initiation using permuted

PROTOCOL TITLE: Comparison of Ambu Auragain and I-Gel Supraglottic Airways in Adult Patients at an Ambulatory Surgery Center

VERSION DATE: 4/3/2021

block randomization with blocks of sizes 2, 4, and 6 used in equal proportion (i.e., 1:1:1) to ensure approximate balance at any point in the study between the two groups. Patients in group 1 will receive an I-gel LMA. Those in group 2 will receive an Ambu Auragain LMA. A standard anesthetic induction will take place using propofol, lidocaine, dexamethasone, and ondansetron. The LMA will be placed by an experienced anesthesia provider. Once absence of lid reflex is confirmed, the LMA will be placed according to instructions from the LMA such that the patient is supine with head in sniffing position. A water-based lubricant will be used on the LMA to ease insertion. The ambu auragain will be inflated to a pressure of 60cmH20. Muscle relaxant will not be used in any patient and maintenance of anesthesia will be with propofol infusion. A research assistant or another anesthesia provider will be in the room to capture all data points. OLP will be measured immediately after insertion. This will be accomplished by closing the expiratory valve while keeping fresh gas flow at 3 liters/minute until equilibrium is reached.

5.2 Study Procedures: Patients will be approached on the day of surgery about participating in the trial. This will be done as soon as they arrive at the ASC to allow adequate time for them to review the study procedures and consent forms. All questions will be answered and patients will be ensured that they have adequate time to review and understand all study procedures. Patients undergoing all surgical procedures with general anesthesia appropriate for an LMA will be eligible to participate. Once enrolled patients will be randomized to one of two groups. Patients in group 1 will receive an I-gel LMA. Those in group 2 will receive an Ambu Auragain LMA. A standard anesthetic induction will take place using propofol, lidocaine, dexamethasone, and ondansetron. The LMA will be placed by an experienced anesthesia provider. Once absence of lid reflex is confirmed, the LMA will be placed according to instructions from the LMA such that the patient is supine with head in sniffing position. A water-based lubricant will be used on the LMA to ease insertion. The ambu auragain will be inflated to a pressure of 60cmH20. Muscle relaxant will not be used in any patient and maintenance of anesthesia will be with propofol infusion. A research assistant or another anesthesia provider will be in the room to capture all data points. OLP will be measured immediately after insertion. This will be accomplished by closing the expiratory valve while keeping fresh gas flow at 3 liters/minute until equilibrium is reached. Once in the recovery room the patient will be asked about a sore throat immediately prior to discharge. Patient will also be called 24 hours after surgery to evaluate sore throat analyzed using NRS 0-10 scale.

Baseline demographics such as surgical procedure, intraoperative opioids, surgical procedure length, BMI, weight, age, and sex will be recorded.

PROTOCOL TITLE: Comparison of Ambu Auragain and I-Gel Supraglottic Airways in Adult Patients at an Ambulatory Surgery Center

VERSION DATE: 4/3/2021

- 5.3 Study Duration: Once ready to discharge from PACU the patient will end study participation with one follow up call on the day after surgery. The study should take 1 month to enroll and another 2 months for study analysis.
- 5.4 Individually Identifiable Health Information: This study does involve PHI, please see combined consent/HIPAA form.
- 5.5 Use of radiation: N/A
- 5.6 Use of Center for Magnetic Resonance Research: N/A

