6.0 Data and Specimen Banking

- 6.1 Storage and Access: All study data will be stored on excel spreadsheets stored in Box. Only the PI and members of the research team will have access to the data.
- 6.2 Data: The data from this study will be collected both from Epic and directly from the patient. The data collected includes: demographic data, age, weight, ASA class, duration of surgery, length of stay in recovery room both phase 1 and 2, time to place LMA, number of attempts, ease of LMA insertion, blood staining, sore throat prior to discharge and at 24 hours post surgically, and any adverse events.

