15.0 Statistical Considerations

15.1 Data Analysis Plan: We plan to collect our data using excel which will be maintained in the box. When the study is completed and ready for statistical analysis the data will be shared with our staff statistician.

15.2 Power Analysis: Previous studies on OLP have shown that there was a mean difference between i-gel and AuraGain in OLP immediately after insertion in pediatrics of -5.9 cmH₂O (95% CI: -8.5 to -3.3) [Mihara EJA 2019 with estimated SD of 4.00 for AuraGel and 8.20 for i-gel] or an estimated mean difference of -1.8 cmH₂O (95% CI: -3.6 to 0.01) [Sabuncu SMJ 2018 with estimate SD of 3.56 for AuraGel and 4.20 for i-gel]. The table below shows the total sample size needed based upon the reported standard deviations from each study to detect a difference of at least 3 cmH₂O in OLP between AuraGel and i-gel:

Power	AuraGel SD	i-gel SD	Total Sample Size
80%	3.56	4.20	56
	4.00	8.20	148
90%	3.56	4.20	74
	4.00	8.20	198

15.3 Statistical Analysis: This study data will be de-identified and shared with our staff biostatistician to be analyzed. The statistician will be provided the protocol so they are able to analyze for primary and secondary objectives.

Continuous data will be summarized with mean (standard deviation) or median (interquartile range) and categorical data will be summarized by

PROTOCOL TITLE: Comparison of Ambu Auragain and I-Gel Supraglottic Airways in Adult Patients at an Ambulatory Surgery Center

VERSION DATE: 4/3/2021

count (percent). Normality will be evaluated with both the Shapiro-Wilk test and graphical evaluation. Univariate comparisons between groups will use t-tests or Mann-Whitney U-tests, as appropriate for normality, to compare continuous variables and chi-squared or Fisher's exact tests to compare categorical variables between groups. Linear regression models will be explored to adjust for variables that are imbalanced after randomization or other covariates that may be clinically relevant.

15.4 Data Integrity: All patients will be assigned a unique patient identifier. The data that will be sent to the statistician will be de-identified.

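### The provider who places the device is not listed among the data to be recorded; a coded provider number would let the planned adjustment use it, for a modest gain in precision

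*Combined protocol and SAP*

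**What the plan says.** On who inserts the device, sections 5.1 and 5.2 use the same sentence: "The LMA will be placed by an experienced anesthesia provider". Experience is not defined, the number of providers is neither given nor limited, and the permuted-block schedule in 5.1 is not described as stratified by provider.

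Two places list what will be collected:

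- Section 5.2: "Baseline demographics such as surgical procedure, intraoperative opioids, surgical procedure length, BMI, weight, age, and sex will be recorded".
- Section 6.2: "The data collected includes: demographic data, age, weight, ASA class, duration of surgery, length of stay in recovery room both phase 1 and 2", followed by insertion, sore-throat and adverse-event items. The sources are stated just before: "The data from this study will be collected both from Epic and directly from the patient".

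Neither list contains provider identity, role or experience, and no other section supplies them.

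On adjustment, section 15.3 says: "Linear regression models will be explored to adjust for variables that are imbalanced after randomization or other covariates that may be clinically relevant". It names no covariate.

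**The concern.** The primary endpoint is the seal obtained just after the device goes in. Four secondary endpoints (time to placement, number of attempts, first-attempt success, ease of insertion) describe the act of insertion. All are partly results of the operator's handling as well as of the device. Variation between operators that is not modelled stays in the residual and widens the interval for the device difference.

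Section 15.3 leaves room for covariates that matter clinically, and the operator is an obvious candidate. A regression can use only what is in the data file, and the plan does not list this variable for collection.

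Two things are at stake. One is some precision on OLP, in a trial sized on an 80% power row. The other is descriptive: without a provider code, nobody can show how many people did the insertions, whether a few did most of them, or how they were spread over the two arms.

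**Working it through.** **Inputs from the documents.** Difference to detect 3 cmH2O; SDs 4.00 (AuraGain) and 8.20 (i-gel); total 148 for 80% power (15.2); 148 enrolled and 165 consented with about 10% dropout (23.1). That gives 74 per arm.

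**Assumptions, not in the documents.** Two-sided alpha 0.05; share *f* of OLP variance lying between providers of 0, 5%, 10% or 20%; number of providers *K* of 10, 20 or 40.

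**Step 1: reproduce the plan's figure.**

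- SE = sqrt((4.00² + 8.20²)/74) = sqrt(83.24/74) = 1.061.
- Noncentrality = 3/1.061 = 2.83.
- Welch noncentral-t power = 80.0%, and 148 is the smallest total that reaches 80%. The normal approximation gives 146.
- The other three rows of the table (56, 74, 198) also reproduce with the t calculation.
- 148/0.9 = 164.4, rounded up to 165, which matches the consent target.

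So no stated figure is in dispute.

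**Step 2: ceiling on the gain.** Suppose the planning SDs contain the operator variance and a provider term removes all of it at no cost. Each SD is then multiplied by sqrt(1 - *f*), and so is the SE.

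| Share *f* | SE | 3/SE | Power (Welch t) | 95% half-width, 1.96 × SE |
|---|---|---|---|---|
| 0 | 1.061 | 2.83 | 80.0% | 2.08 |
| 5% | 1.034 | 2.90 | 82.0% | 2.03 |
| 10% | 1.006 | 2.98 | 84.0% | 1.97 |
| 20% | 0.949 | 3.16 | 88.0% | 1.86 |

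**Step 3: gain when provider effects must be estimated.** The 148 insertions are spread at random over *K* providers. The total variance is the average over arms, 83.24/2 = 41.62, split into a between-provider part 41.62*f* and a residual part 41.62(1 - *f*). The variance of the device effect is the corresponding diagonal element of (X'V⁻¹X)⁻¹, where V has those two components. The components are treated as known, which is slightly generous.

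| Providers *K* | *f* = 5% | *f* = 10% | *f* = 20% |
|---|---|---|---|
| 10 | 81.2% | 82.8% | 86.5% |
| 20 | 80.8% | 82.0% | 85.5% |
| 40 | 80.6% | 81.4% | 83.9% |

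The gain shrinks as *K* grows, because each provider then contributes few insertions and the within-provider comparison carries less information.

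**Step 4: random or fixed provider effects.** With *f* = 0, a random intercept leaves power at about 80%. Fixed effects for 30 providers lower it to about 71%, because they discard the between-provider information and spend degrees of freedom. This is why the fix specifies a random intercept.

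**The case against.** The strongest reply is that the argument rests on silence. The list in 5.2 is introduced by way of example and the one in 6.2 as inclusive, not exhaustive. Section 6.2 leaves out even OLP, the primary endpoint. Epic is a named source, 5.1 puts an observer in the room to record data, and 15.3 is worded broadly enough to admit a provider term. This stands. A reader might infer that the provider will not be recorded and that adjustment is therefore impossible. The documents support only that the provider is not listed and that nothing says it will be extracted.

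A reader might also think that de-identification (15.3, 15.4) keeps the variable from the statistician. It does not: 15.4 describes a unique identifier for patients, and a coded provider number is compatible with it.

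Individual randomisation protects the comparison. Any uneven provider mix between arms is chance imbalance, which the test already allows for. This stands in full.

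The plan also limits operator variation through experienced providers, device instructions, a set head position, lubricant, a fixed AuraGain cuff pressure and a standard induction. The documents give no reason to expect the upper end of the assumed range.

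What remains is narrow: if the variable is not captured, it can be neither adjusted for nor described, and capturing it during the case costs very little.

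**Conclusion.** The point holds as a cheap improvement and does not correct an error. Under the assumed shares of 5%, 10% and 20%, power for 3 cmH2O at 74 per arm goes from 80% to at most 82%, 84% and 88%. With 10 to 40 providers, about 81%, 81-83% and 84-87% is more realistic. If the share is zero, nothing material is gained or lost. The share, the number of providers and the alpha level are assumptions, so the actual size cannot be found from the documents.

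Three stronger readings are tempting and are not supported:

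- **The device comparison is biased.** Allocation is individually randomised, so it is not.
- **148 is too few.** It reproduces exactly from the stated inputs. The planning SDs come from earlier studies and may already contain operator variation, in which case the planned 80% allows for it and adjustment is a bonus. Power would fall below plan only if those SDs excluded operator variation, and nothing in the documents says so.
- **The ceiling figures are the expected gain.** They assume that provider effects are removed perfectly and at no cost.

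**What to change.** 1. Add to the data sheet a coded provider number for each insertion, filled in by the observer already in the room. The key stays out of the file sent to the statistician.
2. In 15.3, name provider as a random intercept in the linear models for OLP and time to placement. Do not use fixed provider effects, which cost power if there are many providers.
3. Report the number of providers and tabulate insertions per provider by arm. For attempts, first-attempt success and ease of insertion, which a linear model does not suit, this table shows the provider mix but does not adjust for it.

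The cost is one extra data column and a slightly more complex model, with no extra patients. The gain in precision shrinks as the number of providers grows and may be negligible; the table of provider mix is useful either way.

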8.0 Study Population

- 8.1 Inclusion Criteria: Adult patients aged 18-80 undergoing outpatient ambulatory surgery under general anesthesia that is amenable to LMA.
- 8.2 Exclusion Criteria: Patients under the age of 18, non-English speaking patients, patients with abnormal airway anatomy
- 8.3 Screening: Patients will be screened by looking at the surgical schedule. They will be contacted by the research team ahead of time and have the study introduced on the morning of surgery. They will have adequate time to evaluate the study and read through the consent and ask questions.

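### No pre-operative sore-throat score is listed, so the two post-operative scores cannot separate pain already present from pain arising after device placement: a cheap, optional precision improvement

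*Combined protocol and SAP*

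**What the plan says.** Section 3.2 names, among the secondary outcomes, "sore throat upon discharge from recovery room and at 24 hours after surgery analyzed using NRS 0-10 scale". It does not define the outcome as new, worsened or changed from baseline.

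Section 5.2 places both assessments after surgery. The first is in the recovery room: "Once in the recovery room the patient will be asked about a sore throat immediately prior to discharge". The second is by telephone: "Patient will also be called 24 hours after surgery to evaluate sore throat analyzed using NRS 0-10 scale". The data list in 6.2 gives the same two time points: "sore throat prior to discharge and at 24 hours post surgically, and any adverse events".

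The baseline list in 5.2 reads: "Baseline demographics such as surgical procedure, intraoperative opioids, surgical procedure length, BMI, weight, age, and sex will be recorded". It has no throat symptom.

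On eligibility, 8.1 admits "Adult patients aged 18-80 undergoing outpatient ambulatory surgery under general anesthesia that is amenable to LMA" and 8.2 excludes "Patients under the age of 18, non-English speaking patients, patients with abnormal airway anatomy". Section 9.1 adds vulnerable groups. None of these concerns a current sore throat. Section 5.2 restates eligibility broadly: "Patients undergoing all surgical procedures with general anesthesia appropriate for an LMA will be eligible to participate".

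Section 15.3 plans univariate comparisons between groups (t-test or Mann-Whitney, chi-squared or Fisher). Linear regression is to be explored for covariates that are imbalanced or clinically relevant.

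**The concern.** A patient who arrives with a throat score of 3 and leaves with 3 is recorded exactly like a patient who arrives with 0 and leaves with 3. Two things follow.

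- The absolute sore-throat levels reported for each device include pain that was there before the device. Randomisation does not remove this, because it affects both arms.
- Pre-existing pain adds between-patient variation to both scores, which widens the confidence interval for the device difference. A baseline score would allow that variation to be adjusted out. The regression in 15.3 cannot use a variable that was not recorded, and nobody could show afterwards that the problem was negligible.

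Sore throat is the only patient-reported outcome among those listed, and 2.1 asks whether one device has a clinical advantage. The score cannot be recovered reliably after surgery, so the decision has to be made before enrolment.

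**Working it through.** **The plan's own figure, to fix the arm size.** Section 15.2 gives 148 in total for leak pressure: difference 3 cmH₂O, SDs 4.00 and 8.20, 80% power. Alpha is not stated; I assume two-sided 0.05. An unequal-variance t calculation returns exactly 148, and also 56, 74 and 198 for the other rows of the table. Section 23.1 allows about 10% dropout: 148/0.9 = 164.4, so 165. Both figures reproduce. That gives 74 per arm. Nothing in this calculation concerns sore throat, which has no stated power target.

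**Assumptions, because the documents give none.** A share p arrives with a sore throat, with p from 1% to 10%. It raises the post-operative score by d = 3 points (d = 2 as a check). The SD is otherwise 2. The comparison is of means.

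**Effect on the score.**

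- Rise in the mean of each arm = p × d
- Added variance = p(1−p)d², taken relative to 2² = 4
- Effective N = 148/(1 + relative increase)

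| p | d | Mean rise, both arms | p(1−p)d² | Relative to 4 | Effective N |
|---|---|---|---|---|---|
| 1% | 3 | 0.03 | 0.0891 | 2.2% | 145 |
| 2% | 3 | 0.06 | 0.1764 | 4.4% | 142 |
| 5% | 3 | 0.15 | 0.4275 | 10.7% | 134 |
| 10% | 3 | 0.30 | 0.8100 | 20.3% | 123 |
| 5% | 2 | 0.10 | 0.1900 | 4.8% | 141 |

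The standard error grows by the square root of the variance ratio: about 1% at p = 1%, 5% at p = 5% and 10% at p = 10%. A comparison that would otherwise have 80% power would have about 79%, 76% and 72%.

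**Chance imbalance is part of this.** With 74 per arm, chance differences between arms in the share affected contribute 2p(1−p)d²/74 to the squared standard error of the device difference. That is the added variance in the table, divided by 74 and doubled for two arms. The probability that the arms differ by 4 or more affected patients is 0.7%, 4%, 18% and 33% at p = 1%, 2%, 5% and 10%. Such a difference would move the device contrast by 4/74 × 3 = 0.16 points, about half of the standard error 2 × √(2/74) = 0.33. The test already allows for this, so it is the same cost seen another way.

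**Effect if sore throat is analysed as yes/no.** The discharge sentence in 5.2 does not itself name the scale, so this form of analysis is possible. If r is the rate arising after placement, the observed rate is p + (1−p)r, and the risk difference is multiplied by (1−p). For assumed rates of 10% and 30%:

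| p | Observed rates | Risk difference | Power, 74 per arm |
|---|---|---|---|
| 0 | 10.0% v 30.0% | 0.200 | 87% |
| 1% | 10.9% v 30.7% | 0.198 | 85% |
| 2% | 11.8% v 31.4% | 0.196 | 83% |
| 5% | 14.5% v 33.5% | 0.190 | 78% |
| 10% | 19.0% v 37.0% | 0.180 | 69% |

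**The case against.** The strongest reply is that this is a precision matter on one of several secondary endpoints. Allocation is 1:1 at random, so pre-existing pain is balanced in expectation and the type I error is preserved. Leak pressure and its sample size are unaffected, and sore throat has no power target to miss. All of that stands, and it is why the point is optional.

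A second reply is that few patients may be affected. Surgery is elective (4.1), patients must be suitable for a laryngeal mask (5.1, 5.2), and they may be withdrawn before surgery for medical reasons (12.1). None of these provisions mentions sore throat, so they do not settle the matter, but they are good reason to include 1% to 2% in the range, where the loss is small.

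A third reply is that the lists in 5.2 and 6.2 are worded as open-ended. That is fair: the documents support saying that a baseline score is not listed, not that nobody will ever ask. It does not supply the score either, since 6.2 gives the sore-throat time points and both are post-operative.

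Finally, the variance formula applies to a comparison of means, while 15.3 allows a Mann-Whitney test, which a bounded 0-10 score may well need. The effective-N figures do not carry over directly to a rank test and should be read as orders of magnitude.

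**Conclusion.** The gap is real and modest. Throat pain present on arrival is not separated from pain arising after placement. This raises absolute levels in both arms and costs some precision that can be neither checked nor adjusted for. Under the stated assumptions (3-point rise, SD 2, prevalence 1% to 10%), added variance is about 2% to 20% and 148 patients carry the information of about 145 to 123. For a yes/no outcome the risk difference shrinks by about 1% to 10%. Prevalence, rise and SD are all assumed.

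A reader might infer that the device comparison is biased, or that the plan attributes all throat pain to the device. The documents support neither: allocation is randomised, and 3.2 describes sore throat at two times without calling it device-caused or new. A reader might also count chance imbalance between arms as a further harm; it is already contained in the added variance.

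Grade: cheap improvement, optional priority.

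**What to change.** - **5.2:** ask the same 0-10 sore-throat question once at consent, before randomisation.
- **6.2:** add the pre-operative score to the data list.
- **15.3:** prespecify it as a covariate for both the discharge and the 24-hour score. If a rank-based test is the main comparison, name a matching adjusted analysis, such as ordinal regression with the baseline score as covariate.

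The cost is one extra question, one data column and one covariate. Research staff already meet the patient before surgery to obtain consent (11.1, 20.1), so no extra visit or staff is needed. The sample size stays at 148, and no change to eligibility is needed. The gain depends on how many patients arrive with a sore throat and how well the baseline score predicts the later ones. If almost all score 0, little precision is gained, but the trial can then show that the issue was negligible.

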12.0 Withdrawal of Participants

12.1 Withdrawal Circumstances: Subjects who have consented and for some reason choose not to participate will be withdrawn and a notation will be made in the study records and these people will be considered screen failures. The surgeon may choose to withdraw the patient from the study prior to surgery for any medical reason or if they suffer a major life-threatening adverse event.

12.2 Withdrawal Procedures: If the patient is withdrawn from study prior to the procedure, they will be noted in study records as screen failures. If they undergo the procedure and they decide they no longer want to be a part of the study or withdrawn by the physician, they will be withdrawn and no further data will be collected. This will also be noted in the study documentation.

PROTOCOL TITLE: Comparison of Ambu Auragain and I-Gel Supraglottic Airways in Adult Patients at an Ambulatory Surgery Center

VERSION DATE: 4/3/2021

12.3 Termination Procedures: If the study is terminated for any reason, or there are more than 5% major adverse events the data that is already collected will be stored in a secure location only accessible to research personnel on this study. No further data will be collected if the study is terminated.

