17.0 Provisions to Monitor the Data to Ensure the Safety of Participants

17.1 Data Integrity Monitoring: The PI, co-investigators, and research assistants will all have access to the study data stored in the University's Box storage system. All the research assistants have experience collecting study information. The PI of the study will periodically review the study data to ensure accuracy and completeness of study data.

17.2 Data Safety Monitoring: The Department of Anesthesiology has established a Data and Safety Monitoring Committee consisting of several staff anesthesiologists which include persons who are board certified as pain specialists. Data will be transmitted in box to persons on the board on a monthly basis for review. If there are patterns of adverse events, the board will meet as needed and provide recommendations.

All safety data will be collected on a case report form and transferred into an excel spread sheet that will be stored in box.

The data will be reviewed on a regular basis (weekly) by the PI and research staff. If there are consistent complications noted a meeting will be convened by the DSMB for recommendations.

The statistician uses R or SAS for analysis of safety data to determine whether harm is occurring. Most likely a regression analysis will be performed to see which event is most likely the contributor for the complications. Also, a chi-square analysis may be performed; all dependent on data variability.

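### The 24-hour call, the only planned contact after discharge, asks about sore throat alone, so later adverse events are captured only passively and the safety count could be too low by an unknown amount

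*Combined protocol and SAP*

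**What the plan says.** Section 5.2 describes the call after surgery as follows: "Patient will also be called 24 hours after surgery to evaluate sore throat analyzed using NRS 0-10 scale". Section 5.3 makes it the only planned contact once the patient has left recovery: "Once ready to discharge from PACU the patient will end study participation with one follow up call on the day after surgery". The secondary endpoints in section 3.2 likewise name sore throat, and nothing else, at 24 hours.

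Adverse events appear elsewhere. The list of data items in section 6.2 ends with "sore throat prior to discharge and at 24 hours post surgically, and any adverse events", and the same section names the sources: "The data from this study will be collected both from Epic and directly from the patient". Section 12.3 sets a threshold beside study termination: "If the study is terminated for any reason, or there are more than 5% major adverse events". Section 17.2 says "All safety data will be collected on a case report form and transferred into an excel spread sheet that will be stored in box", with weekly review by the PI and research staff, monthly transmission to the safety committee, and an analysis by the statistician of whether harm is occurring.

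None of these sections says over what period adverse events are counted or how patients are asked about them. Section 12.3 also leaves open which events are major and what the 5% is a percentage of.

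**The concern.** These are ambulatory patients, so the time between discharge and the next day is spent out of sight of study staff. The one person who speaks to them afterwards is directed, in the section that staff will follow, to a single symptom. An airway problem, or an unplanned return to care at another institution, could go unrecorded unless the patient happens to mention it. What is volunteered depends on the patient and on how the call is conducted, so capture need not be uniform.

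At stake is the safety information that the plan itself relies on: the count behind the 5% threshold, the weekly and monthly reviews, and any statement about harm in the report. Oropharyngeal leak pressure, measured immediately after placement, is not touched.

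**Working it through.** **Step 1. Set the sections side by side.**

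| Element | Where | What is specified |
|---|---|---|
| Sore throat | 3.2, 5.2, 6.2 | Two time points, 0-10 scale, patient is asked |
| Adverse events, collection | 6.2 | Listed; sources are Epic and the patient; no window, no question |
| Adverse events, recording | 17.2 | Case report form; no window |
| Major adverse events, threshold | 12.3 | More than 5%; no window, definition or denominator |
| Contact after discharge | 5.2, 5.3 | One call; stated content is sore throat |

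Sore throat has a time and a method. Adverse events, in the same sentence of section 6.2, have neither. Nothing excludes an event after discharge, but nothing makes anyone look for one. Capture in that period is passive.

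**Step 2. What the 5% threshold means in patients.** Section 23.1 plans 148 enrolled and 165 consented with about 10% dropout; 148 / (1 - 0.10) = 164.4, rounded up to 165, so those two figures agree. Section 12.3 does not say which is the denominator.

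- 0.05 × 148 = 7.4, so the threshold is exceeded at 8 patients (8/148 = 5.4%; 7/148 = 4.7%).
- 0.05 × 165 = 8.25, so the threshold is exceeded at 9 patients (9/165 = 5.5%; 8/165 = 4.8%).

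**Step 3. How much missed events could matter (illustration).** The documents give neither a rate of major adverse events nor the share that would be missed. Both are assumptions here. Let p be the true rate and m the share of major events that appear after discharge and reach the study neither through Epic nor through the patient. The expected observed rate is p × (1 - m). For p = 6%:

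- m = 20%: 0.06 × 0.80 = 0.048
- m = 50%: 0.06 × 0.50 = 0.030

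Both lie below 5% although the assumed true rate is above it.

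The chance that the final count exceeds the threshold is P(X ≥ 8), with X binomial, n = 148 and event probability p × (1 - m):

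| Assumed true rate p | m = 0 | m = 20% | m = 25% | m = 50% |
|---|---|---|---|---|
| 5% | 0.46 | 0.24 | 0.19 | 0.03 |
| 6% | 0.67 | 0.42 | 0.35 | 0.08 |
| 8% | 0.91 | 0.74 | 0.67 | 0.24 |

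With 165 as denominator and 9 as the count, the results are close: at p = 6% they are 0.66, 0.40, 0.33 and 0.06.

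The table shows how sensitive the threshold is to incomplete capture. It does not estimate how many events this trial would miss.

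**The case against.** A reader might infer that adverse events after discharge are not collected at all and that the 5% count covers only the stay in the center. The documents do not support that. Section 6.2 draws on Epic and on the patient with no cut-off at discharge, section 17.2 puts all safety data on a form with no cut-off, and section 12.3 sets no window. An event mentioned on the call or recorded at the site could be counted. For the same reason it cannot be said that the rate is understated, only that it could be.

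Three further points stand.

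- The threshold concerns major events. These are the ones most likely to reach a medical record or to be mentioned unprompted, so large values of m are pessimistic and the lower end of the range is more plausible.
- Adverse events are not among the endpoints in sections 3.1 and 3.2, and section 17.2 describes only a tentative analysis. The plan specifies no between-device comparison of adverse events that could be biased, and nothing in the documents shows that volunteering would differ by device.
- The most obvious throat complaint is already asked about, at discharge and at 24 hours, and a dedicated person records data in the room.

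What the objection does not remove is the absence of a method. A general promise to collect any adverse events does not tell the caller to ask, and an event managed at home or treated elsewhere need not appear in the site's record.

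**Conclusion.** The concern holds in a limited form. Ascertainment after discharge is passive, and the period, the definition of major and the denominator for the 5% count are not stated. The adverse event count could therefore be too low, by an amount that the documents do not allow one to estimate. Under the assumptions shown, even a 20% loss at a true 6% rate lowers the chance of exceeding the threshold from 0.67 to 0.42; if every major event reaches Epic or is volunteered, the loss is zero. The effect is confined to safety monitoring and safety reporting. This is a cheap improvement rather than a flaw in the main comparison.

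**What to change.** - **Sections 5.2 and 5.3:** add to the existing call one scripted open question, worded identically for both groups, on any new problem or unplanned contact with care since discharge. Record the answer on the safety case report form, and let the form separate a patient who was asked and reported nothing from one who was not reached.
- **Sections 6.2, 12.3 and 17.2:** state that adverse events are counted through the end of that call, and state when counting starts.
- **Section 12.3:** state which events count as major and what the denominator is. If it is the 148 enrolled, for example, more than 5% means 8 or more patients. The extra question alone would not make the threshold usable without these two definitions, whose content is for the sponsor to decide.

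The cost is under a minute per call, a short change of wording, and the recording of some minor unrelated complaints. No visit, patient or staff member is added, and no device or clinical procedure changes.
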